#### 3.1. Interim Analyses

Interim PK data was reviewed at dose escalation meeting at each dose by GSK. Non Compartment analyses for Dose Escalation Cohorts was performed using Phoenix Winnonlin version 6.4 or higher under the supervision of clinical Pharmacology Modeling and Simulation (CPMS), GSK.

No N-CRM analysis was performed for the study due to the termination of the study.

#### 3.2. Final Analyses

Final analyses will be performed after all subjects have permanently discontinued study treatment and the final study database is frozen.

See Sections 5 to 16 for details regarding the planned analyses and description of displays to be produced.

## 4. SAMPLE SIZE CONSIDERATIONS

### 4.1. Sample Size Assumptions

The total number of subjects to be enrolled into this study will depend on the number of subjects needed to characterize individual dose cohorts for the determination of the maximum tolerated dose of GSK2820151; the final sample size is not driven by statistical considerations. However, it is anticipated that approximately 30 to 50 subjects will be enrolled with a maximum of 80 subjects.

### 4.2. Sample Size Re-estimation or Adjustment

No sample size re-estimation will be performed.

## 5. ANALYSIS POPULATIONS

### 5.1. All Enrolled Population

The **All Enrolled Population** is defined as all subjects who have consented to participate in the study and have not screen failed.

### 5.2. All Treated Population

The **All Treated Population** is defined as all subjects who receive at least one dose of GSK2820151. Safety and anti-cancer activity will be evaluated based on this analysis population.

### 5.3. PK Population

The **PK Population** will consist of all subjects from the All Treated Population for whom a PK sample is obtained and analysed.

### 5.4. Analysis Datasets

Analysis datasets will be created according to Clinical Data Interchange Standards Consortium (CDISC) version 3.1.3/ Analysis Data Model (ADaM) version 1.0 standards, and data will be listed according to GSK Integrated Data Standards Library (IDSL) reporting standards. Formatting for dates, times, and decimal places will follow GSK standards except where specified.

## 6. TREATMENT COMPARISONS

There are no treatment comparisons in the study.

**6.1. Data Display Treatment and Other Subgroup Descriptors** Unless otherwise stated, all data will be pooled and listed by investigated GSK2820151 dose cohorts.

## 7. GENERAL CONSIDERATIONS FOR DATA ANALYSES

SAS 9.3 or higher version will be used to perform all data analyses and generate listings. Data in the database will be presented in by-subject data listings.

## **8. DATA HANDLING CONVENTIONS**

### **8.1. Premature Withdrawal and Missing Data**

Because study treatment is dependent on the study endpoints (e.g., progression, i.e. not a fixed treatment duration), the length of treatment for each subject will depend on the efficacy and toxicity of the treatment, so the duration of treatment will vary across subjects. Similarly the duration of follow up will also vary. All available PFS data will be analyzed using suitable statistical methods; subjects with shorter treatment and follow-up due to the natural history of their disease or medical necessities of the treatment of their disease will not be considered to have missing PFS data. For endpoints which determine the percentage of responders, subjects with unknown/not evaluable or missing best overall response will be assumed to be non-responders, and will be included in the denominator when calculating the percentages.

In the event that the study is terminated, all available data will be listed.

Missing data occurs when any requested data is not provided, leading to blank fields on the collection instrument. These data will be indicated by the use of a “blank” in subject listing displays. Answers such as “Not applicable” and “Not evaluable” are not considered to be missing data and should be displayed as such.

There will be no other imputation for missing data other than what’s described in [Section 8.2](#) for partial dates and for missing exposure end dates.

### **8.2. Derived and Transformed Data**

The following sections provide a general description of the derived and transformed variables used to describe and analyze the data. Separate analysis dataset specifications provide full details on all data derivations and transformations including descriptions of core standard algorithms and standard oncology algorithms. The analysis dataset specifications will clearly communicate the content and source of the datasets supporting the statistical analyses.

#### **8.2.1. Reference dates**

Unless otherwise stated, the safety reference (start) date will be the start of treatment of GSK2820151. This will also be the efficacy reference date for this study. The reference date for baseline characteristics (e.g. age) will be the date of screening.

#### **8.2.2. Study Day for Safety Measures**

If the date of interest occurs on or after the safety reference date then the safety study day will be calculated as (date of interest - safety reference date) + 1. If the date of interest occurs before the safety reference date then the safety study day will be calculated as (date of interest - safety reference date). There is no safety study day 0.

#### **8.2.3. Study Day for Efficacy**

If the date of interest occurs on or after the efficacy reference date then efficacy study day will be calculated as (date of interest - efficacy reference date) + 1. If the date of interest occurs prior to the efficacy reference date

then efficacy study day will be calculated as (date of interest – efficacy reference date). There is no efficacy study day 0.

#### 8.2.4. Duration and Elapsed Time

Durations (e.g., the duration of an AE, duration of exposure, etc.) are calculated as the stop date minus the start date plus one.

For elapsed time (e.g., the time since initial diagnosis):

- If the reference date is on or after the event date, then the elapsed time is the reference date minus the event date + 1.
- If the reference date is before the event date then the elapsed time is the reference date minus the event date.

When reporting time to event (TTE) durations in months, divide the number of days by 30.4375; to report in weeks divide the number of days by 7; to report in years divide the number of days by 365.25. These algorithms for time to event return decimal numbers, and ignore the actual numbers of days in the months or years between start date and stop date. The "year" used in these algorithms is 365.25 days long, and the "month" is one twelfth of that year.

#### 8.2.5. Imputation of Partial Dates

Imputed partial dates will not be used to derive study day, duration (e.g., duration of AEs), or elapsed time variables. In addition, imputed dates are not used for deriving the last contact date in progression free survival analysis dataset.

Imputed dates will not be displayed in listings. However, where necessary, display macros may impute dates as temporary variables for the purpose of sorting data in listings only. Partial dates may be imputed as outlined below.

The partial date imputation will follow ADaM conventions. The ADaM approach is to populate the numeric date variables with the imputed date and add a flag variable to the dataset that indicates the level of imputation.

The flag variable can contain the values: blank, 'D', 'M', 'Y'.

blank: indicates that no imputation was done

D='Day': indicates that the day portion of the date is imputed

M='Month': indicates that the month and day portions of the date are imputed

Y='Year': indicates that the entire date (year, month, and day) is imputed

Example of Date Variables:

XYZD\_ - character date variable

XYZDT - numeric date variable

XYZDTFL - flag variable

Details on imputing partial dates for specific datasets are outlined below.

**Adverse Events (AE):**

Imputations in the adverse events dataset are used for slotting events to the appropriate study time periods and for sorting in data listings.

Dataset	Date	Missing Element	Rule
Adverse Events (AE)	Start Date	day, month, and year	
 
No Imputation for completely missing dates
 

		day, month	
 
If study treatment start date is missing (i.e. subject did not start study treatment), then set start date = January 1.
 
Else if study treatment start date is not missing:                             
 
If year of start date = year of study treatment start date then                                     
 
If stop date contains a full date and stop date is earlier than study treatment start date then set start date = January 1.
 
Else set start date = study treatment start date.
 
 
 
Else set start date = January 1.
 
 
 

		day	
 
If study treatment start date is missing (i.e. subject did not start study treatment), then set start date = 1st of month.
 
Else if study treatment start date is not missing:                             
 
If month and year of start date = month and year of study treatment start date then                                     
 
If stop date contains a full date and stop date is earlier than study treatment start date then set start date= 1st of month.
 
Else set start date = study treatment start date.
 
 
 
Else set start date = 1st of month.
 
 
 

	End Date		
 
No imputation for partial end dates will be performed
 

**Anticancer Therapy and Radiotherapy, Surgery, Concomitant Medication and Blood and Blood Supportive Care Products:**

Start dates are generally not imputed. If start dates need to be imputed for sorting in data listings, the rules of imputation is defined as below:

Dataset	Date	Missing Element	Rule
Anticancer Therapy	Start Date	day, month, and year	
 
No Imputation for completely missing dates
 

Radiotherapy		day, month	
 
If partial date contains a year only set to January 1st.
 

Surgical Procedures Concomitant Medication Blood and Blood Supportive Care Products		day	
 
If partial date contains a month and year set to the 1st of the month.
 

**Time to Event and Overall Response:**

Start dates for follow-up anticancer therapy, radiotherapy (where applicable), and surgical procedures (where applicable) will be temporarily imputed in order to define event and censoring rules for progression-free survival, response rate, or duration of response (i.e. start date for new anticancer therapy). Dates will only be imputed when a month and year are available but the day is missing. The imputed date(s) will not be stored on the anticancer therapy, radiotherapy, or surgical procedure datasets. The following rules will be used to impute the date when partial start dates are present on anticancer therapy radiotherapy, and/or surgical procedures dataset[s]:

Dataset	Date	Missing Element	Rule
Anticancer Therapy  Where applicable: Radiotherapy  Surgical Procedures	Start Date	day, month, and year	
 
No Imputation for completely missing dates
 

Dataset	Date	Missing Element	Rule
		day, month	
 
No imputation for missing day and month (note the eCRF should only allow for missing day)
 

		day	
 
If partial date falls in the same month as the last dose of study treatment, then assign to earlier of (date of last dose of study treatment+1, last day of month).
 
If partial date falls in the same month as the subject's last assessment and the subject's last assessment is PD, then assign to earlier of (date of PD+1, last day of month).
 
If both rules above apply, then assign to latest of the 2 dates
 
Otherwise, impute missing day to the first of the month.
 

	End Date		
 
No imputation for partial end dates will be performed
 

The date of new anticancer therapy is derived as the earliest date of new anticancer therapy (e.g., chemotherapy), radiotherapy (where applicable), or cancer related surgical procedure (where applicable) and will include imputed dates.

**8.2.6. Imputation of Missing Exposure End Dates**

In general, completely missing dates are not imputed. However, subjects in oncology trials may still be on study treatment when analyses are performed and so may have missing exposure end dates in their last dosing record. Missing exposure end dates will be imputed. For subjects with missing exposure end dates at the time of data cutoff, the exposure end date will be imputed to the earliest of: the date of the data cutoff, the date of withdrawal from the study, or the death date. The imputed exposure end date will be used to calculate cumulative dose and exposure duration. Imputed exposure end dates will be stored on the study treatment end date variable.

**8.2.7. Baseline Definition**

Baseline will be defined as the most recent, non-missing value prior to or on the first study treatment dose date for GSK2820151. For laboratory data, baseline will be defined as the most recent, non-missing value from a central laboratory prior to or on the first study treatment dose date. If there are no central labs collected for a subject and lab test prior to or on the first dose of study treatment, the most recent, non-missing value from a local laboratory prior to or on the first dose of study treatment will be defined as the baseline value.

If the latest pre-dose value is collected on the day of treatment, the time of treatment will be used to identify the baseline value. If the pre-dose time point value is identified as baseline, and the data is recorded in triplicate the average will be used.

For subjects who did not receive study treatment during the study, baseline will be defined as the latest, non-missing collected value.

### **8.2.8. Change from baseline**

Change from baseline will be presented for ECG and ECOG data as described in [Section 11](#).

Change from baseline is calculated as:

- For records occurring after baseline: (visit value) – baseline value.

For the triplicate measurements, the average value will be used as visit value.

Unless otherwise stated, if either the baseline or visit value is missing, the change from baseline and/or percent change from baseline is set to missing as well.

### **8.2.9. Multiple Assessments**

Data from all assessments (scheduled and unscheduled), including multiple assessments, will be included in listings.

### **8.2.10. Actual Treatment**

A subjects' actual treatment will be derived from exposure data.

### **8.2.11. Extended Loss to Follow-up or Extended Time without an Adequate Assessment**

If two or more scheduled disease assessments are missed and are then followed by an assessment of progressive disease (PD) or death, PFS will be censored at the last adequate assessment prior to PD or death. As the scheduled disease assessment is every 8 weeks, a window of 119 days (16 weeks + 7 day window) will be used to determine whether there was an extended time without adequate assessment. That is, if the time difference between PD/death and last adequate assessment is more than 119 days, then PFS will be censored at the last adequate assessment prior to PD/death.

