## **8.6. Efficacy**

The overall response rate is defined as the percentage of subjects with a confirmed complete response (CR) or a partial response (PR) at any time as per RECIST 1.1.

- Lesion assessment will be conducted according to Response Evaluation Criteria in Solid Tumors (RECIST 1.1) [[Eisenhauer, 2009](#)] as outlined below and in [Appendix 8](#).

- Disease assessment modalities may include imaging (e.g., computed tomography [CT] scan, magnetic resonance imaging [MRI], bone scan, plain radiography) and physical examination (as indicated for palpable/superficial lesions).
- The baseline disease assessment will be completed within 2 weeks prior to the first dose of GSK2820151, then every 8 weeks starting W1D1 thereafter, and at the final study visit. See the Time and Events Table (Section 8.1) for the schedule of assessments of anti-cancer activity.
- For subjects with CRPC without measurable disease by RECIST criteria, serial prostate specific antigen (PSA) measurements will be drawn at the disease assessment time points defined in the Time and Events Table (Section 8.1). Response will be defined by the number of subjects who achieve a 50% decrement in their baseline PSA (PSA50).
- Assessments must be performed on a calendar schedule and should not be affected by dose interruptions/delays.
- For post-baseline assessments, a window of  $\pm 7$  days is permitted to allow for flexible scheduling. If the last radiographic assessment was more than 8 weeks prior to the subject's withdrawal from study and progressive disease has not been documented, a disease assessment should be obtained at the time of withdrawal from study.
- Subjects whose disease responds (either complete response [CR] or partial response [PR]) should have a confirmatory disease assessment performed 4 weeks after the date of assessment during which the response was demonstrated. More frequent disease assessments may be performed at the discretion of the investigator.
- To ensure comparability between the baseline and subsequent assessments, the same method of assessment and the same technique will be used when assessing response.

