#### 14.8.4.5. Evaluation of best overall response

The best overall response is the best response recorded from the start of the treatment until disease progression/recurrence and will be determined programmatically by GSK based on the investigators assessment of response at each time point.

- To be assigned a status of SD, follow-up disease assessment must have met the SD criteria at least once after first dose at a minimum interval of 49 days (based on the expected  $56 \pm 7$  day window)
- If the minimum time for SD is not met, best response will depend on the subsequent assessments. For example if an assessment of PD follows the assessment of SD and SD does not meet the minimum time requirement the best response will be PD. Alternatively, subjects lost to follow-up after an SD assessment not meeting the minimum time criteria will be considered not evaluable.

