- If anticancer therapy is started without documented disease progression or is started prior to documented disease progression, then PFS will be censored at the date of the last adequate assessment that is no later than the date of initiation of anticancer therapy (i.e. if an assessment occurs on the same day as the start of new anticancer therapy the assessment will be used - as it will be assumed the assessment occurred prior to the administration of new anticancer therapy). The date of response at the last adequate assessment will be used as the censoring value.

A summary of the assignments for progression and censoring dates for PFS are specified in the following table.

Table 1. Assignments for Progression and Censoring Dates for PFS Analysis

Situation	Date of Event (Progression/Death) or Censoring	Outcome Event (Progression/Death) Or Censored
No ( or inadequate ) baseline tumor assessments and the subject has not died (if the subject has died follow the rules for death indicated at the bottom of the table)	Start Date of Treatment	Censored
No post-baseline assessments and the subject has not died (if the subject has died follow the rules for death indicated at the bottom of the table)	Start Date of Treatment	Censored
Progression documented between scheduled visits	Date of assessment of progression 	Event
No progression ( or death ) and no initiation of new anti-cancer therapy	Date of last ‘adequate’ assessment of response 	Censored
Received subsequent anti-cancer therapy prior to the date of documented events	Date of last ‘adequate’ assessment of response  ( prior to starting initiation of therapy )	Censored
Received subsequent anti-cancer therapy prior to any adequate assessment	Start Date of Treatment	Censored
Received subsequent anti-cancer therapy and no progression ( or death )	Date of last ‘adequate’ assessment of response  ( prior to starting initiation of therapy )	Censored
Death or progression after more than one missed visit	Date of last ‘adequate’ assessment of response  ( prior to missed assessments )	Censored
Death	Date of Death	Event

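### The 119-day test in SAP 8.2.11 can censor a progression after only one missed scan, because it allows the 7-day window at one end of the gap only

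*SAP*

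**What the plan says.** SAP 8.2.11 gives the criterion as a count of scans: "If two or more scheduled disease assessments are missed and are then followed by an assessment of progressive disease (PD) or death", PFS is censored at the last adequate assessment before that event. The matching row of Table 1 in the SAP's PFS section reads "Death or progression after more than one missed visit".

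The same paragraph of 8.2.11 then turns the count into days. It starts from the interval ("As the scheduled disease assessment is every 8 weeks"), sets "a window of 119 days (16 weeks + 7 day window", and ends with the operative test: "if the time difference between PD/death and last adequate assessment is more than 119 days, then PFS will be censored".

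Protocol 8.6 governs the scan dates. Scans are every 8 weeks counted from W1D1; "Assessments must be performed on a calendar schedule and should not be affected by dose interruptions/delays"; and for post-baseline assessments a window of plus or minus 7 "days is permitted to allow for flexible scheduling". Protocol 14.8.4.5 confirms that an early scan counts as on schedule: stable disease requires an assessment "at a minimum interval of 49 days" after first dose, which is 56 less 7.

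**The concern.** The criterion and the test should select the same subjects, and they do not. On a calendar schedule each scan has its own window around its own nominal date, so a gap between two post-baseline scans can be stretched at both ends. The 119-day figure allows for one end only. A subject who missed one scan can therefore exceed 119 days with every attended scan inside its window.

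At stake is how a real progression is recorded. Under the count it is an event on the date of progression. Under the day test it is a censoring at a scan up to 126 days (18 weeks) earlier. Two programmers, one working from Table 1 and one from the last sentence of 8.2.11, could produce different entries for the same subject in Listing 51, the display of PFS, which is part of a secondary endpoint.

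**Working it through.** **Inputs.** Interval 8 weeks = 56 days (SAP 8.2.11, Protocol 8.6). Window w = 7 days either side of each nominal date (Protocol 8.6). Days below are counted from W1D1 as day 0, so nominal scans fall on days 56, 112, 168 and so on.

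**The plan's own figure.** 16 × 7 + 7 = 119. It reproduces.

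**Gap between two on-window post-baseline scans with m scans missed between them:** (m + 1) × 56 ± 2w.

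| Scans missed | Calculation | Gap (days) |
|---|---|---|
| 0 | 56 ± 14 | 42 to 70 |
| 1 | 112 ± 14 | 98 to 126 |
| 2 | 168 ± 14 | 154 to 182 |

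Gaps of 120 to 126 days occur with exactly one missed scan and exceed 119.

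**Example.** The day-56 scan is done on day 49, the day-112 scan is missed, and the day-168 scan is done on day 175 and shows progression. The gap is 175 − 49 = 126 days. The day test censors at day 49; the count of missed scans gives an event at day 175.

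**Where 119 is right.** Treatment start carries no window. Measured from there, one missed scan gives 112 ± 7, or 105 to 119 days, and the threshold fits exactly.

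**Other readings of the schedule.**
- Rolling schedule, with each scan due 56 days after the last actual scan: the one-missed maximum is 112 + 7 = 119. Protocol 8.6 rules this out by requiring a calendar schedule.
- Clinic-visit windows of Protocol 8.2.2 (±3 days to Week 9, then ±5 days to Week 52): a Week 9 scan 3 days early and a Week 25 scan 5 days late give 112 + 8 = 120; ±5 at both ends gives up to 122. Both still exceed 119.
- ±3 days at both ends: maximum 118, so no conflict. That is not the window Protocol 8.6 sets for disease assessments.

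**Deaths.** Let the last adequate scan be a days off its nominal date, with a from −7 to +7. The second missed window closes 112 + 7 − a days after that scan, which is anywhere from 112 to 126 days.
- Last scan on day 56 (a = 0), day-112 and day-168 scans missed, death on day 178. The second window closed on day 175 and the gap is 122 days. The 119-day test censors, as intended; a 126-day test would count an event.
- Last scan on day 63 (a = +7), same two scans missed, death on day 176. Both windows have closed but the gap is 113 days, so the 119-day test does not censor.
- Last scan on day 49 (a = −7), death on day 175. The second window has not yet passed, the gap is 126 days, and the 119-day test censors.

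For deaths, then, any fixed threshold in this range errs in one direction or the other.

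**Share affected, under an assumption.** If the offsets d1 and d2 of the two scans were independent and uniform on −7 to +7, then P(d2 − d1 > 7) = (7² / 2) / 14² = 24.5 / 196 = 0.125. On whole days it is 28 / 225 = 12.4%. Either figure is conditional on progression at the next scheduled scan after exactly one missed scan.

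**The case against.** The best defence is that 119 days has a coherent origin: it is the day on which the second missed window closes, counted from a scan done on its nominal date. It is also exact for gaps from treatment start. The sum is correct, and the section title names extended time without an adequate assessment, so a time-based criterion is no surprise. All of this stands. None of it removes the conflict for a gap between an early post-baseline scan and a late one, because 8.2.11 and Table 1 both state the criterion as a number of missed assessments.

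A reader might infer that 126 should simply replace 119, since two missed scans give at least 154 days. That separation holds only when progression is found at a scheduled, on-window scan. The rule also covers death, and Table 1 provides for progression documented between scheduled visits. The day-178 death above shows that 126 would create a new misclassification.

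The objection on consequence also stands. SAP 1 reports five subjects enrolled and limits output to listings, and SAP 2.1 drops all summary tables and figures, so the Kaplan-Meier summary in Protocol 11.5.2.2 is not produced. Visit-level responses and dates appear in Listing 47, where a reader could see any long gap.

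**Conclusion.** The rule is wrong as written, within limits. For progression found by scan, with the gap starting at a post-baseline scan, a subject with one missed scan and a gap of 120 to 126 days is censored against the plan's own criterion. This follows from the calendar schedule and the ±7-day window and needs no assumption about how scan dates are distributed.

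Two stronger conclusions are not supported. A reader might infer that PFS is biased upward; no PFS estimate is produced, so the effect is at most a wrong entry in Listing 51. A reader might also take 12.5% as the share of PFS events affected. It rests on an assumed uniform scan offset and on exactly one missed scan, and the documents give neither an offset distribution nor a missed-scan rate. Even if all five subjects met that condition, the expected number affected would be 5 × 0.125, or about 0.6. Nothing in the documents shows that any subject had a gap of 120 to 126 days. Severity is minor.

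**What to change.** In SAP 8.2.11, replace the 119-day test with a direct count. Define each scheduled assessment window as its nominal date from W1D1 plus or minus 7 days. Count the windows that closed without an assessment between the last adequate assessment and the progression or death, and censor when the count is two or more. This treats scheduled progression, unscheduled progression and death alike, and it agrees with the Table 1 row as it stands. Apply it to Listing 51.

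The cost is a sentence or two in the SAP, a small change to the PFS derivation, and a check of the scan dates of five subjects. No new data are needed.
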